### 11.2 Sample Size Considerations

Sample size considerations are based on the proportion of subjects with detectable hookworm eggs at any time, as measured by the saturated saline flotation technique. The primary analysis of the proportions will consist of comparing the proportion in each of the three *Na*-GST-1

intervention groups to the proportion in the placebo control group (group 4) using a one-sided Fisher exact test, for a total of three comparisons. The Holm-Bonferroni procedure will be used to control the familywise error rate at 0.05. Based on the results from the initial CHHI trial that was conducted at GWU (NCT01940757), we expect an infected proportion of 90% in group 4 (i.e., infectivity controls), and a proportion less than 20% in at least one of the intervention groups. At alpha=0.05/3, this yields a power of 87.7%. The power is 73.2% for an infection rate of 30% in intervention and 96.3% for an infection rate of 10%.

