- c. The proportion of subjects with detectable hookworm eggs in each of the intervention groups (Groups 1, 2 and 3) will be compared to the proportion of subjects in the placebo control group (Group 4) using a one sided Fisher exact test. The p-values from the three tests will be adjusted using the Holm-Bonferroni procedure to control the familywise error rate at 0.05. Power calculations are based on this outcome.

Primary Objective #2: To evaluate the safety and reactogenicity of Na-GST-1/ Alhydrogel® delivered with or without AP 10-701 or CpG 10104 on Days 0, 56 and 112, in healthy, hookworm-naïve adults.

AEs will be coded according to Medical Dictionary of Regulatory Activities (MedDRA™) preferred terms. The frequency, severity, and relationship of AEs per each vaccine formulation of Na-GST-1 will be presented in tabular form using the MedDRA™ coded term and organized by MedDRA™ System, Organ, and Class (SOC) designations.

1. The frequency of solicited local injection site and systemic AEs, and unsolicited AEs will be summarized by SOC and preferred term.
2. Line listings of clinical and laboratory AEs classified as solicited injection site, solicited systemic, or unsolicited and will be displayed in tables stratified by formulation group (i.e., Na-GST-1/Alhydrogel, Na-GST-1/Alhydrogel plus AP 10-701, Na-GST-1/Alhydrogel plus CpG 10104, or saline placebo).
3. AEs will be summarized by severity and relationship to vaccine by individuals and formulation of Na-GST-1.
4. The frequency of vaccine-related SAEs and AESIs will be tallied as well as summarized by body system, by vaccine formulation.

*Primary Outcome #2 Measures:*

The following summary parameters will be evaluated for each formulation of Na-GST-1, in comparison to saline placebo control:

1. Frequency of solicited injection site and systemic reactogenicity, graded by severity, on the day of each study vaccination through 14 days after each study vaccination.
2. Frequency of solicited adverse events, graded by severity, on the day of CHHI through study Day 280.
3. Frequency of study vaccine-related Serious Adverse Events from the time of the first study vaccination through approximately 10 months after the last study vaccination.
4. Frequency of clinical safety laboratory adverse events.

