### 3. DATA ANALYSIS CONSIDERATIONS

#### 3.1 Determination of Sample Size

Sample size considerations are based on the proportion of subjects with detectable hookworm eggs at any time, as measured by the saturated saline flotation technique. The primary analysis will consist of comparing the proportion of subjects in each of the three *Na*-GST-1 vaccination groups (groups 1, 2 and 3) to the proportion of subjects in the placebo control group (group 4) using a two-sided Fisher exact test, for a total of three comparisons. Targeting a rate of 90% subject hookworm infection as observed in the 50 *Na*-L3 dose cohort and a greater than 80% rate of protection in at least one of 3 vaccination groups (e.g., different doses or adjuvant formulations) compared to controls that did not receive the hookworm vaccine, a sample size of 48 (12 per group) would be sufficient to demonstrate the efficacy of a prophylactic hookworm vaccine such as *Na*-GST-1 or *Na*-APR-1, with alpha ~ 0.1 and power of at least 80% [[name] et al, OFID, April 2018].

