### **5.7.4 Primary and Secondary Analysis**

#### **5.7.4.1 Primary Endpoint Analysis**

The primary efficacy endpoint analysis of proportion of subjects with detectable hookworm eggs in fecal samples, at any time point post-CHHI, will be summarized using frequency counts and percentages as a descriptive measure at time points post-CHHI for all vaccination groups.

Along with the summaries for any time points post-CHHI, the proportion of subjects with detectable hookworm eggs in fecal samples will be summarized as a descriptive measure by study group at each time point.

The proportion of subjects with detectable hookworm eggs in each of the vaccination groups (Groups 1, 2 and 3) will be compared to the proportion of subjects in the placebo control group (Group 4) using a two-sided Fisher exact test. The p-values for the pairwise comparison of proportions of subjects in the vaccination groups (Group 1, 2 and 3) and placebo group (Group 4) will be reported. No adjustments for multiple comparisons will be made and therefore, the reported p-values will have to be interpreted with caution.

The proportion of subjects with at least one injection site AE and the frequency of the AE grouped by PT will be compared by *Na*-GST-1 vaccine formulation and placebo. The null hypotheses that the type and number of adverse events is the same across all groups will be tested using Fisher's exact test.

Laboratory results (haematological and clinical chemistry) will be descriptively examined and any clinically significant values for individuals will be reported.

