#### **7. CHANGES OF ANALYSIS FROM PROTOCOL**

The analysis point no. 2 in the analysis plan section secondary outcome #2 and #3 measures performs the ANOVA. Hence analysis Section “e” (Protocol Version 4.0 Page no.72) is not required if it is not specific to three-way ANOVA.

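### The SAP's primary efficacy test conflicts with the protocol's one-sided, Holm-adjusted rule and sets no success threshold

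*SAP*

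**What the plan says.** **Protocol.** Section 11.2 compares each of the three vaccine groups with placebo "using a one-sided Fisher exact test, for a total of three comparisons", and adds: "The Holm-Bonferroni procedure will be used to control the familywise error rate at 0.05". Section 11.4, Primary Objective #1, item c repeats the test ("in the placebo control group (Group 4) using a one sided Fisher exact test") and the adjustment ("The p-values from the three tests will be adjusted using the Holm-Bonferroni procedure to control the familywise error rate at 0.05"), and says the power calculations rest on this outcome. The planning assumption is "we expect an infected proportion of 90% in group 4 (i.e., infectivity controls), and a proportion less than 20% in at least one" of the vaccine groups. The stated power at alpha 0.05/3 is 87.7%, with 73.2% and 96.3% for vaccine-group infection rates of 30% and 10%.

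**SAP.** Sections 3.1 and 5.7.4.1 make the same three comparisons with a two-sided Fisher test. Section 5.7.4.1 reports the pairwise p-values and states: "No adjustments for multiple comparisons will be made and therefore, the reported p-values will have to be interpreted with caution". It names no significance level. Section 3.1 justifies 12 per group "with alpha ~ 0.1 and power of at least 80" per cent. Section 7, the place for changes from the protocol, has one entry: "The analysis point no. 2 in the analysis plan section secondary outcome #2 and #3 measures performs the ANOVA", so that a three-way ANOVA item may be dropped. Sidedness, the Holm step and alpha are not mentioned there.

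**The concern.** A primary endpoint needs one prespecified decision rule. Here the protocol has a complete one, and the SAP replaces it with an analysis that has no rule. Someone working from the SAP has to pick a threshold: the general 5% level in Protocol 11.4, or the figure of about 0.1 in SAP 3.1.

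The choice has consequences. Protocol 2.2.1 says the challenge model is meant to let the most promising formulation be selected for paediatric testing, and Protocol 2.2.5 makes further testing depend on this trial indicating efficacy of at least one formulation. The protocol's power figures belong to its own rule, not to an unadjusted two-sided analysis. The SAP's power figure is tied to an alpha that its analysis section never adopts.

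**Working it through.** **Inputs.** 12 subjects per group, three comparisons with placebo, and infection rates of 90% (placebo) and 20%, 30% or 10% (vaccine), all from Protocol 11.2 and the protocol summary. The 0.05 and 0.10 thresholds for the SAP analysis are assumptions, because SAP 5.7.4.1 gives none.

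**1. The protocol's power.** Exact power is the sum of Bin(x; 12, p_vaccine) × Bin(y; 12, p_placebo) over all tables whose Fisher p-value is at or below alpha.

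| Vaccine infection rate | Stated | One-sided, 0.05/3 | Two-sided, 0.05/3 |
|---|---|---|---|
| 20% | 87.7% | 88.8% | 86.7% |
| 30% | 73.2% | 74.1% | 68.1% |
| 10% | 96.3% | 97.6% | 97.3% |

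The one-sided rule reproduces all three figures to within 2 points; the two-sided version misses at 30%. The protocol's power therefore belongs to its one-sided rule. At 90% against 20%, per-comparison power is 88.8% under that rule, 94.6% at unadjusted two-sided 0.05 and 98.1% at unadjusted two-sided 0.10.

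**2. One dataset under each rule.** Take placebo 12/12 and vaccine arms 7, 8 and 8 of 12. When every placebo subject is infected, the one-sided p-value for x infected in a vaccine arm is C(12, 12−x) / C(24, 12−x).

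- x = 7: C(12,5)/C(24,5) = 792/42,504 = 0.0186
- x = 8: C(12,4)/C(24,4) = 495/10,626 = 0.0466

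With equal arms the two-sided p-value is double: 0.0373 and 0.0932.

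- Protocol: the first Holm step needs p ≤ 0.05/3 = 0.0167. Since 0.0186 > 0.0167, **0** formulations are named.
- Unadjusted two-sided 0.05: only 0.0373 qualifies, so **1**.
- Unadjusted two-sided 0.10: all three qualify, so **3**.

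**3. How often the rules disagree.** All outcomes were enumerated with placebo at 90% and all vaccine arms at 60% infected (an illustrative intermediate effect). The number of formulations named differs from the protocol's in 14% of trials at two-sided 0.05 and 38% at two-sided 0.10. At least one formulation is named in 36% (protocol), 45% (0.05) and 65% (0.10) of trials. The exact 0/1/3 split has probability 0.9%.

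**4. False claims of benefit.** Under a common infection rate p, the familywise error is Σ_y P(Y = y) × [1 − (1 − r(y))³]. Here y is the placebo count and r(y) is the chance that one vaccine arm is declared better given y. For Holm, any rejection requires at least one p ≤ 0.05/3. Maximised over p from 0.01 to 0.99:

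| Rule | Maximum familywise error, benefit direction |
|---|---|
| Protocol: one-sided, Holm 0.05 | 1.4% |
| Two-sided 0.05, unadjusted | 3.0% |
| Two-sided 0.10, unadjusted | 7.9% |

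**5. Direction of the difference.** The SAP analysis is not always the more liberal one. With placebo 12/12 and vaccine arms 2, 2 and 8, the third Holm step tests 0.0466 against 0.05 and passes, so the protocol names three. Unadjusted two-sided 0.05 compares 0.0932 with 0.05 and names two.

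**The case against.** The strongest defence is that this is an early-phase trial. SAP Section 1 says it informs a larger study, so a type I error would not make an ineffective vaccine available. Protocol 11.1 seeks an indication of impact, Protocol 2.2.5 leaves progression to sponsor review of the full study report, and the SAP openly says it makes no adjustment. All of that is true. It does not settle the matter, because the protocol chose formal familywise control for this same trial and the SAP neither follows that choice nor says that it departs from it.

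Other parts of the defence limit what can be concluded:

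- A reader might infer that the protocol's error control is lost. Counting errors in either direction, the unadjusted maxima are 6.0% and 15.8%, but those are not comparable with the protocol's benefit-only 1.4%. Like for like, the figures are 3.0% and 7.9%. False benefit claims exceed 5% only if 0.10 is the decision threshold.
- A reader might infer that 0.10 is the SAP's rule. The documents do not say so: it appears only in the sample-size sentence, which is worded generically and rests on a publication. If it were the rule, the SAP's claim of at least 80% power would hold (98.1% at 20% infected).
- A reader might infer that the sponsor concealed a change. The SAP is tied to protocol Version 4.0 (25 September 2019). The protocol supplied carries a November 2025 IRB stamp and lists three secondary objectives against the SAP's six. Whether Version 4.0 already had the Holm rule cannot be checked here.

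**Conclusion.** The point stands as a conflict between the two documents together with a missing success threshold in the SAP. It is wrong as written, whichever text came first, and should be resolved before unblinding. The main harm is that the number of formulations called effective is not fixed in advance; gross error inflation is not shown. The 14% and 38% disagreement rates rest on the assumed 90% and 60% infection rates and on the 0.05 and 0.10 thresholds supplied for the SAP analysis. The 0/1/3 example shows what is possible, not what is typical.

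**What to change.** Rewrite SAP 3.1 and 5.7.4.1 to the protocol rule: three one-sided Fisher exact tests against placebo, Holm-adjusted p-values reported, familywise error 0.05. Delete the alpha of about 0.1 and the sentence declining adjustment. With the protocol rule restored, its stated power applies again.

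If a departure is intended, amend the protocol before unblinding, state the decision threshold, list the change in SAP Section 7 and restate power for the new rule.

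The cost is wording only. The smallest p-value will usually rise (0.0373 two-sided becomes 3 × 0.0186 = 0.056 in the 7, 8, 8 example). Others may fall because the test is one-sided (0.093 becomes 0.047 for the third arm in the 2, 2, 8 example).

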#### 5.7.4.2 Secondary Endpoint Analysis

Fecal egg counts of the subjects in each of the vaccination (Groups 1, 2 and 3) and placebo (Group 4) groups will be assessed for normality. If normality assumption is confirmed, the comparison between vaccination groups (Group 1, 2 and 3) and placebo group (Group 4) will be done using T-test. Otherwise, the vaccination groups (Group 1, 2 and 3) will be compared with the placebo group (Group 4) using a Wilcoxon-Mann-Whitney rank-sum test. Continuous data will be summarized using the descriptive statistics (mean, median, minimum, maximum and median 95% CI). Mean or Median differences and corresponding 95% CIs will be computed for each pairwise comparison.

Time to patent infection (i.e., the first timepoint at which hookworm eggs are detectable in a fecal sample) will be displayed using Kaplan-Meier estimates, with log-rank tests used to compare the distribution of time-to-patency between groups and censoring of early withdrawals or those failing to develop patent infection.

The detectable anti-*Na-GST-1* IgG responses will be summarized as a descriptive measure using descriptive statistics (mean, standard deviation, median, minimum and maximum) for each observed measurement by vaccination groups and placebo. IgG levels will be displayed graphically by study group using time series and notched box plots at each time points.

Geometric mean antibody responses will be compared between vaccination groups and placebo at each time point using an ANOVA model. An ANOVA model will be fitted with IgG responses as the dependent variable and vaccination groups and placebo as independent variables. The estimated geometric least square means and geometric least square means difference from the model, 2-sided *p*-value and 95% CI for vaccination groups compared to placebo group will be constructed and presented for each time point.

Percent change in IgG antibody levels from days of vaccination to days 7, 14 and 28 post-vaccination, as well as percent change in IgG antibody levels from the peak following the third vaccination to 1, 2, 4, 6, 7, 8, and 10 months post-vaccination will be summarized using descriptive statistics (mean, standard deviation, median, minimum, maximum and 95% CI) for each observed measurement along with the percent change from baseline.

A longitudinal model will be built to describe the IgG levels over time. Using a longitudinal panel model, differences in antibody isotype levels by vaccination groups and placebo will be explored. The analysis will take account of the correlation between measurements on the same subject. A mixed model repeated measure (MMRM) will be fitted with IgG levels as the dependent variable and vaccination groups and placebo, visits and interaction between groups and visits as independent variables. the estimated geometric means Standard Error and geometric means difference from the model, 2-sided *p*-value and 95% CI for vaccination groups and placebo will be constructed.

Logistic regression will be explored for the binary response of hookworm infection post-CHHI as a function of antibody response. Dependant variable will be the hookworm infection status (Positive/Negative) and independent variable will be the IgG responses and vaccination groups and placebo. Estimated number of subjects, Standard Error and odds ratio from the model, 2-sided *p*-value and Wald 95% CI for vaccination groups and placebo will be constructed.

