5. Frequency of unsolicited adverse events, graded by severity, from the time of each study vaccination through approximately 1 month after each study vaccination; and from the time of CHHI through treatment with albendazole (Day 297).

6. Frequency of new-onset chronic medical conditions through approximately 10 months after the third study vaccination.
7. Frequency of Adverse Events of Special Interest through approximately 10 months after the third study vaccination.

*Analysis Plan:*

- a. The proportion of subjects with at least one injection site AE will be compared by Na-GST-1 vaccine formulation. We will test the null hypotheses that the type and number of adverse events is the same across all groups by Fisher's exact test.
- b. We will test the null hypothesis that the frequency of adverse events grouped by SOC term is the same in all groups using exact Poisson tests of the ratio of the rates. There will be no adjustment for multiple comparisons.
- c. Laboratory results (hematological and clinical chemistry) will be examined for trends over time and any clinically significant values for individuals will be reported.

Secondary Objective #1: To compare the impact of vaccination with Na-GST-1/Alhydrogel® delivered with or without AP 10-701 or CpG 10104 on fecal egg counts, as determined by the McMaster method, after CHHI with *N. americanus* larvae in healthy, hookworm-naïve adults.

*Secondary Outcome #1 Measure:*

The following parameters will be evaluated for each formulation of Na-GST-1, in comparison to the saline placebo control:

1. Fecal egg counts as determined by microscopy using the McMaster method, during Weeks 5 through 20 post-CHHI.

*Analysis Plan:*

- a. Fecal egg counts as determined by microscopy of the subjects in each of the intervention groups (Groups 1, 2 and 3) will be compared to the eggs counts of the subjects in Group 4 using a Wilcoxon-Mann-Whitney rank-sum test. The p-values from the three tests will be adjusted using the Holm-Bonferroni procedure to control the familywise error rate at 0.05.

Secondary Objective #2: To assess the relationship between antibody responses to Na-GST-1 induced by vaccination with Na-GST-1/Alhydrogel® delivered with or without AP 10-701 or CpG 10104 and responses to CHHI in healthy, hookworm-naïve adults, as determined by the presence of eggs using a qualified flotation technique.

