##### **4.2 Secondary Outcome Measures**

The following parameters will be evaluated for each formulation of *Na*-GST-1, in comparison to the saline placebo control:

1. Fecal egg counts during Weeks 5 through 20 post-CHHI.
2. The anti-*Na*-GST-1 IgG antibody response (ELISA) at approximately 14 days after each vaccination, and approximately 1, 2, 4, 6, 7, 8 and 10 months after the third dose.

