## 5. STATISTICAL METHODOLOGY

### 5.1 General Considerations

The statistical analyses will be performed by Quartesian Clinical Research, using SAS Version 9.3 (or higher). All tables, figures and listings will be produced in landscape format. In general, all data will be listed by the subject and visit/time point where appropriate.

Data will be summarized by time-point where appropriate. The total number of subjects in the study group (N) under the stated population will be displayed in the header of summary tables.

Data will be summarized using descriptive statistics for continuous variables. Unless otherwise stated, descriptive statistics will include number of subjects, mean, standard deviation, minimum, median and maximum for all endpoints in case of  $n < 2$ , where n indicates the number of evaluable subjects at the particular time point, only n, mean, minimum and maximum will be displayed. The statistic "Missing" will also be evaluated by enumerating the number of missing entries/subjects, if any at that visit, and presented along with summary statistic. Display NC if any value is not computable.

Decimal Precision Convention: The minimum and maximum statistics will be presented to the same number of decimal places as the original data. The mean and median will be presented to one more decimal place than the original data, whereas the standard deviation will be presented to two more decimal places than the original data.

For categorical variables, counts and percentages will be used. The count [n] indicates the actual number of subjects with non-missing value at particular visit or actual number of subjects with that event or category, which should always be less than or equal to the total number of subjects in the respective study group [N]. Percentage will be obtained by:  $\% = (n/N) * 100$ .

Unless otherwise stated, all percentages will be expressed to one decimal place.

Also, the distributions for continuous variables will be examined for normality using Shapiro-Wilk tests. If any deviation in the normality assumption is judged, then the data will be analyzed using appropriate non-parametric tests.

The following conventions will be applied to analyses/data presentation:

All dates will be displayed in DDMMYY format.

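### For fecal egg counts the SAP lets a normality check choose the test and states no Holm step, against the protocol, and neither document reduces ten counts per subject to one value

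*SAP*

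**What the plan says.** **Protocol 11.4, Secondary Objective #1.** Each of Groups 1, 2 and 3 is compared with the "eggs counts of the subjects in Group 4 using a Wilcoxon-Mann-Whitney rank-sum test". Then: "The p-values from the three tests will be adjusted using the Holm-Bonferroni procedure to control the familywise error rate at 0.05". There is no pre-test, and sidedness is not stated.

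**SAP 5.7.4.2.** Egg counts in the vaccination and placebo "groups will be assessed for normality". The rule continues: "If normality assumption is confirmed, the comparison between vaccination groups (Group 1, 2 and 3) and placebo group (Group 4") is a t-test; failing that, it is Wilcoxon. For output: "Mean or Median differences and corresponding 95% CIs will be computed for each pairwise comparison". SAP 5.1 names the check ("the distributions for continuous variables will be examined for normality using Shapiro-Wilk tests") but gives no significance level. Nothing is said about multiplicity for egg counts. The sentence "No adjustments for multiple comparisons will be made and therefore, the reported p-values will have to be interpreted with caution" stands in SAP 5.7.4.1 and refers to the primary comparison.

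**SAP Section 7** (changes from protocol) lists one item, on the three-way ANOVA for IgG.

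**Endpoint.** SAP 4.2 has only "Fecal egg counts during Weeks 5 through 20 post-CHHI". Protocol 3.2.2 and 11.4 add the McMaster method. Neither names a mean, maximum, area under the curve or visit.

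**Dates.** The SAP (15 June 2020) cites protocol Version 4.0 of 25 September 2019. The protocol supplied carries an IRB approval date of 11/17/2025.

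**The concern.** Three defects of unequal weight sit in one short paragraph of the SAP.

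1. The two documents prescribe different tests and different error control for the same endpoint, and the SAP's own list of changes is silent on it.
2. The effect measure follows the branch taken. The SAP does not say what happens if one group passes the normality check and another fails, so the three formulations could be reported on different scales in a trial meant to compare them.
3. A t-test or rank-sum test needs one independent value per subject, and the schedule yields ten. Whoever programs the analysis must choose the reduction, and nothing requires that choice to be made before the data are seen.

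The stakes are practical. Protocol 2.1.4 expects the vaccine to act by killing worms or lowering their fecundity. Lower fecundity would show in egg counts but could be missed by a primary endpoint that asks only whether any egg was ever seen. Protocol 2.2.1 and 2.2.5 use the trial to choose among formulations, and make further testing depend on at least one showing efficacy. That is a decision across a family of three comparisons.

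**Working it through.** **1. Counts per subject.** Protocol 7.3 schedules post-challenge, pre-treatment fecal samples on Days 175, 182, 189, 203, 217, 231, 245, 259, 273 and 280. With challenge on Day 140, (day − 140)/7 gives Weeks 5, 6, 7, 9, 11, 13, 15, 17, 19 and 20. That is 10 counts per subject and 12 × 10 = 120 per group. Testing by visit would mean 10 × 3 = 30 tests.

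**2. Inputs.** From the documents: four groups of 12, a shared placebo group, 90% expected infected in placebo (Protocol 11.2), and subject means of 0 to 133 epg in the earlier 50-larvae cohort (Protocol 2.1.9.1). The documents give no SD, within-subject correlation or McMaster counting unit, so these are assumed. Null simulation: overdispersed Poisson counts, 10% never infected, mean 50 epg if infected, between-subject log-SD 0.5 to 1.0, counting unit 1, 25 or 50 epg, plus a purely normal case. The SAP rule was coded as Shapiro-Wilk at an assumed 0.05 in both groups of a pair, then t-test, otherwise Wilcoxon, two-sided 0.05. There were 3,000 trials per scenario (1,500 for pooled counts, 500 for by-visit tests). The Monte Carlo standard error at a 12% familywise rate is √(0.12 × 0.88/3000) = 0.6 points.

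**3. The plan's own figure.** The only operating figure for this endpoint is the protocol's 5% familywise rate. One value per subject (mean, maximum or a single visit), Wilcoxon and Holm gives 3.1% to 4.9%, so the protocol's method delivers what it states.

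**4. Pre-test and Holm, one value per subject.**

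| Procedure | Per comparison | Familywise, three tests |
|---|---|---|
| SAP rule, egg-count-like data | 4.3–5.3% | 10.8–13.5% |
| SAP rule, normal data | 5.5–5.8% | 13.2–14.3% |
| Wilcoxon, no Holm | 4.0–4.9% | 10.3–12.5% |
| Wilcoxon with Holm | – | 3.1–4.9% |

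For reference, three independent tests give 1 − 0.95³ = 14.3%. Comparing rows 1 and 3, removing the pre-test changes little; comparing rows 3 and 4, Holm changes a great deal. The t-test branch is taken in 0% to 61% of egg-count-like comparisons, so the reported effect scale is far from settled in advance.

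**5. If all samples were pooled as independent.** With 10 samples per subject and correlation ρ, the variance of a group mean is understated by 1 + 9ρ. At ρ = 0.22 this is 2.98, and 1.96/√2.98 = 1.14, so the actual two-sided error is about 26%. At ρ = 0.50 it is 5.5, and 1.96/√5.5 = 0.84, about 40%. Simulated Wilcoxon error per comparison was 28% to 46%, with a familywise rate of 56% to 80%, and still 41% to 68% after Holm. A second simulation (log-normal, median 40 epg, correlation 0.3 and 0.6, 50 epg per egg seen) gave 25% and 31%, against 4.3% and 4.5% for Wilcoxon on subject means.

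**6. If each visit were tested.** Wilcoxon at all ten visits, unadjusted, gives a 47% to 69% chance of at least one false positive among 30 tests, although each single test is near nominal.

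**7. The harms do not add up.** Under the second set of assumptions (log-SD taken as 1.0), both groups passed Shapiro-Wilk in 47% and 23% of data sets on subject means but in 0% on pooled counts. The t-test branch therefore matters only once counts have been reduced, and there the two-stage rule rejected 4.8% to 4.9%.

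**The case against.** The strongest reply is that nothing here shows an invalid p-value. The pre-test leaves each comparison near its nominal level. Without Holm, each p-value can still be read singly. No document calls for pooling: both compare the counts of subjects, and Protocol 2.1.9.1 reports mean egg counts over all collected samples from the earlier challenge study, which makes a subject mean the natural reading. By-visit testing is also only an inference, since SAP 5.7.4.2 specifies every time point for IgG but not for egg counts. This reply stands. A reader might infer from the 25–46% figure that the planned p-values are invalid; the documents do not support that. The analysis is undefined, and a natural reading is not a rule.

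Second, SAP Section 1 says type I error matters less because no ineffective vaccine would be released on these results. That is a stated position, but it does not remove the conflict with the protocol's 5% control, and the results still select a formulation.

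Third, a reader might infer that the SAP authors dropped Holm without saying so. This cannot be shown. The SAP was written for Version 4.0, and the protocol supplied may differ from it: affinity, memory B cells and innate responses are secondary objectives in the SAP and exploratory in this protocol. The Holm text may be later.

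Finally, egg count should not be called the only quantitative efficacy measure. Fecal PCR (Protocol 3.2.3), expelled worm counts (Protocol 8.2.3.2) and time to patency (SAP 5.7.4.2) are also planned.

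**Conclusion.** The point holds in a limited form. The current protocol and SAP conflict on the egg-count test and its error control, and SAP Section 7 does not explain it. Under assumed distributions, the SAP rule gives a familywise error of about 11–14% where the protocol promises 5%. The absent Holm step accounts for most of that; the pre-test's cost is an effect measure chosen by the data.

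The missing per-subject summary is a gap in both documents and leaves the two-sample test undefined. Serious inflation follows only under pooling, and multiplicity of 30 tests only under by-visit testing; neither is prescribed.

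The textual findings need no assumptions. The error rates depend on assumed spread, correlation, counting unit and Shapiro-Wilk level, but the two main simulations agree in direction and broadly in size. It should be settled before unblinding.

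**What to change.** In **both** Protocol 11.4 and SAP 4.2/5.7.4.2:

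- Define the endpoint as each challenged subject's mean epg over the scheduled Week 5–20 samples, with negative samples counted as 0 and uninfected challenged subjects included.
- State the rule for subjects treated or withdrawn early. Otherwise their means rest on early, possibly pre-patent samples.
- Compare each vaccine group with placebo by Wilcoxon, state the sidedness, and apply Holm over the three tests as the protocol says.
- Report one fixed effect measure with a 95% CI, for example the Hodges-Lehmann shift.
- Delete the normality pre-test and the t-test branch for this endpoint.

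Record any remaining difference in SAP Section 7, against the protocol version actually in force. Settle it together with the SAP's unadjusted primary comparisons, since Holm on a secondary endpoint beside an unadjusted primary would be hard to explain. A maximum or a single visit would control error equally well; the mean is suggested because Protocol 2.1.9.1 already reports it and Protocol 2.2.5 plans mean egg counts for the first pediatric Phase 2 trial.

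Cost: wording, one derived variable, a line defining the challenged set (SAP 5.3 has none), and slightly less power per comparison, because Holm's first threshold is 0.05/3 = 0.0167.
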